2.4 Exploratory Analysis

This exploratory analysis will only be conducted if requested by the funding agency after considering results from individual trials, Aim 3 and Aim 4 analyses. Following the completion of both the parent and supplement studies' planned analyses, we will conduct a secondary analysis to estimate outcome differences among the 4 arms (parent study-nurse visit, parent study-control, supplement study-phone call, and supplement study-control) using generalized linear models. Since the supplement did not enroll patients from the neurology/neurosurgery/yellow team, subjects from these service units will be excluded from this exploratory analysis. In addition, since the supplement did not enroll during the winter months, subjects with index discharge dates in the months of November through April will be excluded from this exploratory analysis. Next we will compare demographics, clinical characteristics and outcomes by state (OH and KY) and by CCHMC location (main and Liberty). If there are no meaningful differences between groups, we will include both OH and KY and main and Liberty in this exploratory analysis. If meaningful differences are observed, the analysis will be further restricted to comparable groups of subjects. The analysis will begin by comparing demographic/clinical characteristics among the four groups (parent study-nurse visit, parent study-control, supplement study-phone call, and supplement study-control); variables that differ meaningfully will be retained as covariates in the multivariable models. Although we will assess for potential differences between the studies, we expect that the characteristics of individual studies will be very comparable in terms of patient population due to randomization and due to identical study processes and data collection/capture methods. For the PDCS and return to normal routine, we will use multivariable linear regression models. The primary independent variable will be a 4-level categorical variable of treatment arm assignment (i.e., parent study- nurse visit, parent study-control, supplement study-phone call, supplement study- control). This will allow us to estimate the difference in outcome between the nurse visit and phone arm by utilizing contrasts from the model. We will estimate least square means which can be thought of as linear combinations of the parameter estimates constructed to correspond to average predicted values in a population where the levels of classification variables are balanced, i.e. treatment arm assignment. For the 30-day utilization outcome, we will use a multivariable logistic regression model, specifying the logit link, and again the 4-level categorical variable indicator of treatment arm assignment will be the independent variable of interest. For this outcome, our interest is in estimating the difference in proportion along with 95% confidence intervals between the nurse visit and phone arms. As above, we will utilize contrasts from the model and least square means. The proportion of false discoveries will be controlled using an appropriate multiple comparisons adjustment.

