Enrolled patients and their families will be randomized 1:1 after discharge to the intervention group or standard-of-care using a permuted block randomization stratified by acute versus chronic underlying illness and hospitalist service general vs. surgical service to ensure equal allocation of the intervention within each stratification block. Random permutations within each block within each stratum will be generated using a random number generator available in SAS Proc Plan. The use of randomization in the study design is crucial for avoiding bias in the evaluation of the effectiveness of the nurse home visit intervention. Patients and families cannot be blinded given that the nature of the intervention is a nurse home visit. However, we will attempt to mitigate the potential bias in the following manner: 1) Families will be asked to refrain from disclosing intervention status to the interviewer at the follow-up phone call; and 2) Study staff will be blinded to treatment assignment when making the follow-up phone call. Study staff will use a written script to administer the survey. At the start of the call, families will be reminded to refrain from disclosing their intervention status.

Heterogeneity of Treatment Effects:

We have multiple planned analyses to examine potential heterogeneity of treatment effect of the nurse visit. Factors included in the HET analysis are insurance, primary care access, financial strain, caregiver education, hospital service, and medical complexity. Medical complexity will be determined by the pediatric medical complexity algorithm (PMCA). The PMCA is a publicly available algorithm that identifies children with complex chronic disease (who have accessed tertiary hospital care). The algorithm includes three levels of medical complexity: children with complex chronic disease (C-CD), children with non-complex chronic disease (NC-CD), and children without chronic disease (CD). In order to calculate the PMCA we will collect additional administrative data for all patients enrolled in Aims 3 and 4. This data will include: ICD9 Codes/ICD10 codes, procedure codes, admission date, discharge dates, admitting and discharge departments. We will capture all outpatient, urgent care, ED, and hospital events within the specified time window (February 1, 2012 to April 30, 2016). The PMCA will be calculated based on a 3-year window before the index hospitalization.

Aim 4

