Enrolled patients and their families will be randomized 1:1 after discharge to the intervention group or standard-of-care using a permuted block randomization stratified by home state of residence (Ohio vs. Kentucky) to ensure equal allocation of the intervention within each stratification block. Random permutations within each block within each stratum will be generated using a random number generator available in SAS Proc Plan. The use of randomization in the study design is crucial for avoiding bias in the evaluation of the effectiveness of the nurse phone call intervention. Patients and families cannot be blinded given that the nature of the intervention is a nurse phone call. However, we will attempt to mitigate the potential bias in the following manner: 1) Families will be asked to refrain from disclosing intervention status to the interviewer at the follow-up phone call; and 2) Study staff will be blinded to treatment assignment when making the follow-up phone call. Study staff will use a written script to administer the survey. At the start of the call, families will be reminded to refrain from disclosing their intervention status.

Post-Hoc Analysis

Qualitative Analysis: The post-hoc analysis of this proposal will use qualitative methods, specifically interviews and focus groups. At the completion of the post-hoc analysis, we will have an improved understanding of the experiences, challenges, and successes of pediatric inpatient-to-outpatient transitions from the perspective of families and providers. Qualitative methods are the best means to generate consensus themes about patient and family experiences and preferences during inpatient-to-outpatient transitions. Interviews will be used to gain insight into what families and providers believe to be both the most relevant barriers to successful transition and the outcomes they find to be most meaningful. Participants will respond to semi-structured interviews and focus groups. The interviewer will use follow-up probes to expand and clarify responses and further elucidate the context of the responses. This qualitative methods process will permit us to gain unique perspectives and understand more deeply our results.

Readmission Analysis:

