Inclusion criteria for Aims 1-3 are that the patient must be under 18 years of age and be admitted to either the Hospital Medicine Service at Base or Liberty, the Surgical Hospital Medicine Service at Base, the Adolescent Medicine Service at base, the Community Pediatrics Service, Neurosurgery Service, or the Neurology Service. **Exclusion criteria** for Aims 1-3 are if

	YR 1 2014			YR 2 2015				YR 3 2016				YR 4 2017			
Project Tasks	Q2	Q3	Q4	Q1	Q2	Q3	Q4	Q1	Q2	Q3	Q4	Q1	Q2	Q3	Q4
Aim 1: Focus groups; complete transcription															
Aim 2: Quality Improvement project															
Aims 3 & 4: Randomized Control Trials; Post Hoc analysis															
Data cleaning and Data analysis															
Develop and implement dissemination strategy															

the patient is discharged to a residential facility, their home residence is outside the home nursing service area (in Ohio within 55 miles of Base), if they are eligible for "traditional" home care services, or if the caregiver is non-English speaking.

Inclusion criteria for Aims 4 is that the patient must be under 18 years of age and be admitted to either the Hospital Medicine Service at Base or Liberty, the Adolescent Medicine Service at base, or the Community Pediatrics Service. They must live in Ohio within 55 miles of Base or in Kentucky Counties Boone, Kenton, or Campbell. **Exclusion criteria** for Aim 4 is if the patient is discharged to a residential facility, if they are eligible for "traditional" home care services, or if the caregiver is non-English speaking.

Inclusion criteria for the qualitative post-hoc analysis is that the patient must be admitted to either the Hospital Medicine Service at Base , the Adolescent Medicine Service at base, the Community Pediatrics Service at base, or the Neurosurgical services. The parents must reside within the home nursing service area (in Ohio within 55 miles of Base). Exclusion criteria for post-hoc analysis includes if the caregiver or provider is non-English speaking , if the patient is admitted for a mental health reason (e.g. suicidal ideation), or if the patient is admitted for sexually transmitted infection.

Aim 1

We anticipate conducting 3 focus groups per socioeconomic strata, resulting in 9 groups with 6-8 parent/guardian participants within each group. Previous focus group work has shown that not all

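### The four-arm exploratory analysis may keep Kentucky children, who were ineligible for Aim 3, so state is partly confounded with trial in the visit-versus-phone contrast

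*SAP*

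**What the plan says.** **Eligibility (Protocol, Selection & Recruitment of Participants).** The exclusions "for Aims 1-3 are if", among other things, "their home residence is outside the home nursing service area (in Ohio within 55 miles of Base"). No Kentucky exception is given. For Aim 4 the residence rule is wider: "They must live in Ohio within 55 miles of Base or in Kentucky Counties Boone, Kenton, or Campbell".

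**Randomization (Protocol, Study Design).** Aim 4 is "stratified by home state of residence (Ohio vs. Kentucky"). Aim 3 is "stratified by acute versus chronic underlying illness and hospitalist service general vs. surgical service", with no state factor.

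**Four-arm analysis (SAP 2.4).** Where only one trial enrolled a group, the SAP removes it. For services: "Since the supplement did not enroll patients from the neurology/neurosurgery/yellow team, subjects from these service units will be excluded from this exploratory analysis". Index discharges from November through April are removed on the same reasoning. Residence is handled by a look at the data instead. Demographics, clinical characteristics and outcomes are compared by state and by hospital location, and then "If there are no meaningful differences between groups, we will include both OH and KY and main and Liberty in this exploratory analysis". The fallback is: "If meaningful differences are observed, the analysis will be further restricted to comparable groups of subjects". Neither what counts as meaningful nor what makes groups comparable is defined.

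**Status (SAP 1.7 and 2.4).** The analysis runs only if the funding agency asks for it, after the planned analyses of both trials are complete.

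**The concern.** The visit-versus-phone contrast is a between-trial comparison. Randomization balances the arms within each trial. It does not make the Aim 3 visit arm comparable with the Aim 4 phone arm, although SAP 2.4 cites randomization as a reason to expect comparability. Shared eligibility is the main design safeguard, and the SAP uses it for service and season but not for state. Kentucky is the mirror image of the excluded services: enrolled in the supplement and ineligible for the parent trial.

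Three things follow:

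- The phone arm may be a mix of Ohio and Kentucky while the visit arm is Ohio only.
- The check that decides whether to keep Kentucky can easily miss a moderate difference, because failing to see one in a small group does not show comparability.
- Because the check includes outcomes and comes after both trials have been analysed, observed results help to choose the population.

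**Working it through.** The plan gives no figure to reproduce. The core of the point is a comparison of eligibility rules; the arithmetic only illustrates its size.

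**Step 1. Overlap by eligibility**

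| Factor | Parent (Aim 3) | Supplement (Aim 4) | Rule in SAP 2.4 |
|---|---|---|---|
| Neurology, neurosurgery, yellow team | enrolled | not enrolled | removed outright |
| November-April discharges | not removed at source | not enrolled | removed outright |
| Kentucky residents | ineligible | eligible (three counties) | kept unless states look different |
| Liberty site | eligible | eligible | kept unless sites look different |

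By eligibility, the Kentucky share is 0% in both parent arms. Liberty is listed for both trials, so it does not share the problem.

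**Step 2. What a model can and cannot recover**

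Ohio children are in all four arms. If the state effect is the same in every arm on the model's scale, a state term removes it from the arm contrasts. That term is estimated from the supplement alone, since the parent arms have no Kentucky children. Whether a home visit works differently in Kentucky cannot be estimated at all.

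**Step 3. How often the state check would miss a difference**

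Inputs:
- total N = 900 (SAP 1, planned enrollment);
- event rate 20% (Protocol, Aim 4 sample size);
- state difference of 7.1 points, borrowed from the Aim 4 target effect in the same section, which was set for a 750/450 design and serves here only as a yardstick;
- Kentucky share of 10%, 20% or 30%, **assumed**;
- a two-sided 5% significance test, **assumed**, since SAP 2.4 specifies none.

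Formulas:
- SE = sqrt(0.2 × 0.8 × (1/n_KY + 1/n_OH))
- 95% half-width = 1.96 × SE
- difference detectable with 80% power ≈ 2.8 × SE
- power ≈ Φ(7.1/SE − 1.96), with SE in points

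| Kentucky share | n_KY / n_OH | SE (points) | Half-width | Detectable at 80% | Power for 7.1 points |
|---|---|---|---|---|---|
| 10% | 90 / 810 | 4.44 | 8.7 | 12.4 | Φ(−0.36) = 36% |
| 20% | 180 / 720 | 3.33 | 6.5 | 9.3 | Φ(0.17) = 57% |
| 30% | 270 / 630 | 2.91 | 5.7 | 8.1 | Φ(0.48) = 68% |

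A calculation that takes Ohio at 20% and lets Kentucky be higher is slightly less favourable: detectable differences are 13.3, 9.9 and 8.7 points, and power for a 7-point difference is 36%, 53% and 64%.

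**Step 4. Shift in the contrast if state is left out of the model**

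Shift = Kentucky share of the phone arm × (Kentucky rate − Ohio rate).

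- 7-point difference: 0.10 × 7 = 0.7; 0.20 × 7 = 1.4; 0.30 × 7 = 2.1 points.
- 2-point difference: 0.2, 0.4 and 0.6 points.

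Using 7.1 instead of 7 gives the same results to one decimal.

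**Step 5. After restriction to Ohio**

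The Kentucky share is 0 in all four arms, so this imbalance is 0. The remaining sample size cannot be computed because the documents give no Kentucky count.

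**The case against.** The strongest reply is that SAP 2.4 already has protection. It uses multivariable models for every outcome and keeps as covariates those characteristics that differ meaningfully among the four groups. State of residence is on the SAP 2.3.1 list of baseline characteristics. With Kentucky absent from two arms, state is an obvious candidate. With state in the model and an additive effect, the shift in Step 4 disappears. This stands in part: the 0.7-2.1 points describe an analysis without state, which the SAP allows but does not prescribe. State is not named as a covariate in SAP 2.4, and adjustment leaves the visit-by-state question open.

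A second reply is that the SAP speaks of meaningful differences, not significant ones, so a 7-point gap might be acted on whatever its p-value. That is fair. The power figures show how noisy the comparison is, not that it must fail. With no threshold defined, however, nobody can say in advance what would trigger the restriction.

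A third reply concerns stakes. The analysis is exploratory, conditional on a request, and has a fallback restriction. Even 2.1 points is under half of the contrast's own 95% half-width, which is about 4.9-5.8 points if 450 phone children are compared with 600 or 300 visit children (assumed) at a 20% rate: 1.96 × sqrt(0.16 × (1/450 + 1/600)) = 4.9 and 1.96 × sqrt(0.16 × (1/450 + 1/300)) = 5.8. This stands and limits the severity.

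**Conclusion.** The point holds, at low to modest severity. SAP 2.4 applies the shared-eligibility principle to service and season but not to state, and it lets outcomes by state help to decide who is analysed. The eligibility argument needs no assumption. The size does: 36-68% power for a 7.1-point state difference, and a shift of about 0.7-2.1 points for a 7-point difference, rest on an assumed 10-30% Kentucky share, a 20% event rate, a significance test and, for the shift, a model without state.

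Four stronger readings are tempting, and the documents do not support them:

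- *State is wholly confounded with trial.* It is not, because Ohio is in all four arms.
- *The check cannot detect a difference as large as the trial's target effect.* At 20% and 30% Kentucky the half-widths (6.5 and 5.7 points) are below 7.1. The check would often miss such a difference, not always.
- *Main versus Liberty has the same defect.* Both trials list Liberty.
- *The Aim 4 results are compromised.* The Aim 4 primary analysis compares randomized arms within one trial and includes state in the model (SAP 2.3.2).

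**What to change.** In SAP 2.4, replace the conditional rule for state with wording such as:

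> Kentucky residents were not eligible for Aim 3. The main four-arm analysis is therefore restricted to Ohio residents. Outcomes by state will not be used to decide inclusion. A sensitivity analysis may include Ohio and Kentucky residents, with state of residence as a prespecified covariate.

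If the sensitivity analysis is reported, it should say that the state effect comes from the supplement alone and that a visit-by-state effect is not estimable. The rule for hospital location is a separate and lesser matter; both trials enrolled at Liberty, so no restriction is needed on overlap grounds.

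The cost is a change of SAP wording, or a justified deviation under SAP 2.1.1. Kentucky children leave the main version of an optional analysis, and intervals for the supplement arms become slightly wider. The Aim 4 primary analysis does not change.

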
Appendix: Data Management Plan

Data sources:

- 1) Interview data entered into REDCap (Research Electronic Data Capture)
- 2) EHR data (EPIC is the EHR system used at CCHMC) labeled CSV files transmitted via SFTP
- 3) HealthBridge labeled CSV files transmitted via SFTP
- 4) Home Care Epic database
- 5) HNCC Care Management participation
- 6) Readmission risk stratification data (data coming from [name])
- Interview data at discharge and 14-days, including patient medical record number, will be
 entered into REDCap and stored on SQL secured servers hosted by CCHMC's Biomedical
 Informatics (BMI) division, with state of the art security features including audit trails and
 password protection.
- For patients enrolled in the supplement, select CCHMC EPIC data fields, including patient demographics, index admission characteristics, readmission, revisit data within 30-days of discharge, and nurse phone visit characteristics (for the intervention arm only), will be extracted from the EHR EPIC system by CCHMC BMI staff and sent to CCHMC Data Management Center (DMC).
- HealthBridge routinely receives inpatient and emergency department admission and discharge information from hospitals across the Greater Cincinnati-Dayton community. As of January 1, 2015, all the local hospital systems (except for VA) were part of HealthBridge, which includes the hospital based free standing emergency units/urgent care. Using a patient panel provided by CCHMC DMC of patients enrolled in the supplement, HealthBridge will match and track admission information for these patients. Healthbridge has an automatic patient match rate of 98.2%. Of the remaining 1.8%, 99.5% of those have suggested matches that are staff reviewed and linked. The remaining records are reviewed and manually matched by staff. A complete file will sent to CCHMC DMC every 6 months.
- The data sources will be linked together using CCHMC patient medical record number. The statistical software SAS will be used to import and merge data sources and to create analysis datasets. This will be done by CCHMC DMC.
- We will use guidelines set by Clinical Data Acquisition Standards Harmonization (CDASH) version
 1.1, whenever possible for data collection fields. This standard guideline includes recommended
 data collection fields for 18 domains; including demographics, adverse events and other
 common domains that are common to most therapeutic areas and phases of clinical research.
- Ongoing data quality reports will be generated by the study data manager and will include data completeness, measured as the percentage of required variables completed divided by the expected required fields. In addition, descriptive statistics will be run to identify obvious errors in the database.
- During data collection, all associated research data will be physically stored on a password-protected secure sever maintained by CCHMC, except HealthBridge, which will follow their established standards until data is transferred to CCHMC. No data will reside on portable or laptop devices.
- Data collected during this study will be archived by CCHMC DBE in a study specific virtual archive folder.

•

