We have multiple planned analyses to examine potential heterogeneity of treatment effect of the nurse visit. Factors included in the HET analysis are insurance, primary care access, financial strain, caregiver education, hospital service, and medical complexity. Medical complexity will be determined by the pediatric medical complexity algorithm (PMCA). The PMCA is a publicly available algorithm that identifies children with complex chronic disease (who have accessed tertiary hospital care). The algorithm includes three levels of medical complexity: children with complex chronic disease (C-CD), children with non-complex chronic disease (NC-CD), and children without chronic disease (CD). In order to calculate the PMCA we will collect additional administrative data for all patients enrolled in Aims 3 and 4. This data will include: ICD9 Codes/ICD10 codes, procedure codes, admission date, discharge dates, admitting and discharge departments. We will capture all outpatient, urgent care, ED, and hospital events within the specified time window (February 1, 2012 to April 30, 2016). The PMCA will be calculated based on a 3-year window before the index hospitalization.

Aim 4

Analyses: For the primary outcome, the dependent variable will be a dichotomized indicator of any occurrence of healthcare reutilization within 30 days of hospital discharge. Differences between phone intervention and control groups on this outcome will be evaluated using logistic regression with census tract poverty and discharge service unit included in the model. Other potential covariates (e.g. baseline characteristics with large differences between groups) will be included in a secondary analysis model evaluating the effectiveness of the phone intervention. For secondary outcomes, PDCS total score and number of days back to normal routine perceived by the caregiver at 14-day post-discharge will be analyzed as continuous variables. Differences between the phone intervention and control groups will be evaluated using linear regression with census tract poverty and discharge service unit and other potential covariates included in the model.

Sample size: Assuming a 20% reutilization rate in the control group, a sample size of 750 in the control group and 450 in the phone intervention group will achieve 80% power to detect a 7.1% decrease in reutilization rate (12.9% event rate) for the phone call intervention group with alpha=0.05, allowing for 11% noncompliance.

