2.3.1 Description of study population

Sample size:

The total number of patients who are screened, consented, randomized, and withdrawn will be given. A summary of patients with protocol violations, such as failed nurse phone call, or who were withdrawn will be provided.

Demographics and Clinical Characteristics, Patient and Parent:

Demographic and clinical characteristics as measured at baseline will be summarized by trial arm. Variables to be summarized are: child age, only child indicator, first hospitalization indicator, parent or caregiver age, race/ethnicity, education, marital status, household income, employment status, primary payor, financial strain, access to primary care, census track poverty (high vs. low percentage below poverty), state of residence (Ohio vs. Kentucky). Primary discharge diagnosis ICD9 or ICD10 codes will be categorized using the AHRQ CCS algorithm. Variables will be summarized using descriptive statistics appropriate for each type of data item.

Baseline characteristics with large differences between groups will be included in analyses evaluating the effectiveness of the intervention.

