2.3.2 Primary outcome analysis

Primary outcome: unplanned re-hospitalization and/or any emergency/urgent care visits within 30 days of hospital discharge

For the primary outcome, the dependent variable will be a dichotomized indicator of any occurrence of unplanned re-hospitalization and/or any emergency/urgent care visits within 30 days of hospital discharge recorded in CCHMC Epic or Healthbridge for non-CCHMC events. Differences between intervention and control groups on this outcome will be evaluated using logistic regression with the stratification variables (census tract poverty and state of residence). Other potential covariates (e.g. baseline characteristics of age, first hospitalization, only child, caregiver education, with large differences between groups) will be included in a secondary analysis model evaluating the effectiveness of the intervention.

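### The SAP lists readmission-risk data as a source but no Aim 4 analysis names them; if they are a baseline measure, prespecify them in the primary model, for a modest and conditional gain in power.

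*SAP*

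**What the plan says.** The Data Management Plan in the SAP appendix gives six data sources. The sixth is "Readmission risk stratification data". No variable, scale, assignment date or completeness is given. The item does not reappear in the baseline summary (2.3.1), the primary model (2.3.2), the secondary models (2.3.3), the subgroups (1.3, 2.3.4) or the four-arm exploratory analysis (2.4).

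The SAP primary analysis is a "logistic regression with the stratification variables (census tract poverty and state of residence", and those two factors are its only covariates. The protocol's Aim 4 analysis differs: "logistic regression with census tract poverty and discharge service unit included in the model". Neither model contains a risk measure.

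Further covariates are chosen by imbalance. SAP 2.3.1 states: "Baseline characteristics with large differences between groups will be included in analyses evaluating the effectiveness of the intervention". SAP 2.3.2 places such covariates in a secondary model and gives an open list of examples; readmission risk is not among them.

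For the pediatric medical complexity algorithm (PMCA), the protocol says "we will collect additional administrative data for all patients enrolled in Aims 3 and 4". The SAP does not mention PMCA.

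**The concern.** In a randomised trial, adjusting for a baseline variable that predicts the outcome increases the power of the treatment test in logistic regression and introduces no confounding. The SAP primary model holds one socioeconomic and one geographic factor and nothing clinical. By contrast, the Aim 3 analysis includes chronic illness and hospital service.

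The imbalance rule does not fill the gap. A strongly prognostic variable that happens to be balanced would never enter, while a weak one that happens to be unbalanced would. The rule also leaves the covariate set open until the arms have been compared.

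At stake is some efficiency in the primary comparison, not its validity. A model with only the stratification factors is unbiased and conventional.

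**Working it through.** **Inputs.** From the protocol's Aim 4 sample size: control rate 20%, phone rate 12.9% (a 7.1-point difference), alpha 0.05, 11% noncompliance, 80% power, and "a sample size of 750 in the control group and 450 in the phone intervention group". From SAP section 1: 900 patients randomised 1:1, so 450 per arm. A two-sided test is stated only for the secondary outcomes and is assumed here. The measure's AUC for the primary composite is not given; 0.60 to 0.75 is assumed.

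**Step 1: reproduce the stated power.** Treat noncompliance as dilution: 0.89 × 7.1 = 6.32 points, so 20% against 13.68%. With Δ = 0.06319,

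Power = Φ{[Δ − 1.96·√(p̄(1−p̄)(1/n₁+1/n₂))] / √(p₁(1−p₁)/n₁ + p₂(1−p₂)/n₂)}

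For 750/450: p̄ = 0.1763; the null SE is 0.02272 and the alternative SE is 0.02181. (0.06319 − 0.04454)/0.02181 = 0.855, so power is **80.4%**. The same formula needs 743 controls against the 750 stated. The protocol's figure reproduces under this reading. With no allowance for noncompliance, power would be 89.3%; with both arms cut by 11%, 85.5%.

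**Step 2: same assumptions at the SAP's size.** For 450/450: p̄ = 0.1684; the SEs are 0.02495 and 0.02486. (0.06319 − 0.04890)/0.02486 = 0.575, so power is **71.7%**.

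**Step 3: add a baseline risk score.** 4,000 trials per setting were simulated with one normal risk score, marginal rates held at 20% and 13.68%, and a Wald test of the arm coefficient without and with the score.

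| Assumed AUC | Explained variation | 750/450: without → with | 450/450: without → with |
|---|---|---|---|
| 0.50 | 0% | 80.4 → 80.3 | 70.8 → 70.7 |
| 0.60 | 2.1% | 81.6 → 82.1 | 71.5 → 72.0 |
| 0.65 | 4.6% | 79.7 → 81.6 | 72.0 → 73.1 |
| 0.70 | 8.7% | 80.9 → 83.9 | 72.5 → 75.3 |
| 0.75 | 14.5% | 80.8 → 85.9 | 72.3 → 77.9 |

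At 450 per arm the simulation error per figure is √(0.72 × 0.28/4000) = 0.7 points. Both models are fitted to the same trials, so the difference is steadier than that. A second simulation (5,000 to 6,000 trials per setting, 450 per arm) gave about 72% rising to 74% at AUC 0.65, 75% at 0.70 and 78% at 0.755. For a three-level tier it gave 72% to 74% (AUC 0.66) and 71% to 78% (AUC 0.74).

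**Step 4: express the gain in patients.** At AUC 0.70 and 450 per arm, (1.960 + 0.684)²/(1.960 + 0.598)² = 6.991/6.543 = 1.068, worth about 0.068 × 900 ≈ 60 patients.

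**Step 5: timing.** The protocol's Aim 4 design randomises after discharge, so a value fixed at or before index discharge predates assignment. The documents do not say whether this measure is fixed by then.

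**Step 6: PMCA as a substitute.** Its data window runs from February 1, 2012 to April 30, 2016, with a 3-year look-back. Enrollment was to end October 31, 2016 (SAP section 1), with none from November through April (SAP 2.4). Discharges from May to October 2016 would therefore lose up to 6 of 36 months of look-back. The data would still precede randomisation.

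**The case against.** The strongest objection is that the covariate is unknown. One line in a data inventory does not show that the measure predates randomisation, covers all patients or predicts the outcome. An inventory is not an analysis specification: source 5, care-network participation, is also in no SAP model, although the protocol intends it as a covariate. This stands, and it makes the recommendation conditional.

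A reader might infer that the measure predicts the main component of the primary outcome. The protocol's own figures (Aim 3 sample size) do not support that: 5% readmission on the general service against 10% ED revisits. Against a 20% composite, readmission is at most about 5/20, or a quarter, and urgent care visits also count. What matters is the AUC for the composite. For illustration, with assumed AUCs of 0.70 for readmission and 0.55 for other events, 0.25 × 0.70 + 0.75 × 0.55 = 0.59, where the gain is about half a point. The lower rows of the table cannot be presumed.

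The simulation also leaves out the strata already in the model, so any overlap between risk and poverty would shrink the gain. And the open covariate provisions in SAP 2.3.1 to 2.3.3 could admit the measure, so the accurate statement is that no analysis names it, not that none could use it.

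None of this defeats the request to define the measure and settle its role in advance.

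**Conclusion.** The point holds in conditional form. A potentially prognostic variable is listed as a source, no planned analysis names it, and the route by which it could enter depends on chance imbalance.

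At 450 per arm, power of about 72% would rise by about 0.5 to 1 point at AUC 0.60, 1 to 2 at 0.65, 3 at 0.70 and 5 to 6 at 0.75. It would not rise at all if the measure is not prognostic. This rests on the diluted effect, a two-sided test, assumed AUCs, a measure fixed before randomisation and near-complete data.

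A reader might conclude that the trial is giving up power as a matter of fact, or that this change would repair its power. The documents support neither. The loss depends on properties they do not state, and adjustment does not restore 80% anywhere in the assumed range. The conflict between 750/450 in the protocol and 900 randomised 1:1 in the SAP is a separate and larger matter.

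**What to change.** In the SAP, define the readmission-risk measure: its source tool, categories, time of assignment and completeness. Then:

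- **If it is fixed at or before index discharge and nearly complete:** in 2.3.2, make the primary model a logistic regression on arm, the randomisation strata and the risk category. Use the same covariates for the two secondary re-utilization outcomes in 2.3.3. Give missing values their own category, and report the strata-only model as a sensitivity analysis.
- **If it is not a pre-randomisation measure:** keep it out of the model and state that it is descriptive only. PMCA level may replace it only if its data window is extended past April 30, 2016, or the truncated look-back is stated.

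While editing, reconcile the protocol's discharge service unit with the SAP's state of residence in the primary model.

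The cost is a few lines of SAP text and one covariate from data already listed; extending the PMCA window would need a further extract. A small downside is that the odds ratio becomes conditional on risk category and is not directly comparable with the strata-only odds ratio, so the two should be shown side by side.
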